## Division & Personnel

### Division

What Area Group does the PI belong to?  
What Division/Department does the PI belong to?  
Geriatric Psychiatry  
Within the division/department, what Center or group are you affiliated with, if any?  
program on healthy aging and late life brain disorders

## Amendment

Describe the change(s) being made

We are amending our compensation schedule to increase study time point compensation for the baseline and end point MRI scans from \$50 to \$125. For completing each scan, participants will receive \$125, totaling at \$250 for the completion of both scans.

These changes are reflected in the recruitment materials attached, the PSF section 'Compensation and/or Reimbursement', and the attached CF.

We are also adding QR codes to recruitment materials. These QR codes lead to a previously approved (by [name]) Qualtrics survey where participants can enter their contact information and indicate that they agree to have research staff contact them for more information.

This protocol contains all language recommended through the institution's COVID-19 re-opening guidelines and was previously approved to restart recruitment.

Provide the rationale for the change(s)

We have received feedback from current and past participants that the compensation for the time spent completing assessments for the protocol could be improved. As a direct response to this feedback, we are increasing the compensation for the completion of MRI visits at baseline and end point. We believe that this increase will help better offset time spent completing study assessments.

We are adding QR codes to recruitment materials to potentially improve the odds of successfully reaching interested participants.

Comment on the extent to which the proposed change(s) alter or affect risks/benefits to subjects

N/A

Comment on if the proposed change(s) require a modification to the Consent Form (CF)

The proposed changes require a modification to the CF. Please find the updated version of the CF attached. All changes are also reflected in the compensation and/reimbursement section of the PSF.

## Procedures

**To create the protocol summary form, first indicate if this research will include any of the following procedures**

- ✓ Psychiatric Assessment
- ✓ Neuropsychological Evaluation
- ✓ Medication Trial
- ✓ Use of Placebo or Sham Treatment
- ✓ MRI
- ✓ Somatic Treatment or Intervention

## Population

**Indicate which of the following populations will be included in this research**

- ✓ Adults over 50

## Research Support/Funding

Will an existing internal account be used to support the project?

No

Is the project externally funded or is external funding planned?

Yes

Select the number of external sources of funding that will be applicable to this study

2

## Funding Source #1

Is the PI of the grant/contract the same as the PI of the IRB protocol?

Yes

Select one of the following

The grant/contract application is a pending review or a funding decision

Source of Funding

Federal

Institute/Agency

National Institute on Aging

Grant Name

Sensation and Psychiatry: Linking Age-Related Hearing Loss to Late-Life Depression and Cognitive Decline

Grant Number

R21AG059130

Select one of the following

Single Site

Business Office

RFMH

Does the grant/contract involve a subcontract?

Yes

Subcontracted?

To

Name institution(s)

Columbia University

## Funding Source #2

Is the PI of the grant/contract the same as the PI of the IRB protocol?

No

Who is the PI of the grant/contract?

[name]

Select one of the following

The grant/contract is currently funded

Source of Funding

Industry

Sponsor

Phonak, Inc (donation of hearing aids only, no money)

Is the study investigator initiated?

Yes

Select one of the following

Single Site

Business Office

CU

Does the grant/contract involve a subcontract?

No

## Study Location

Indicate if the research is/will be conducted at any of the following

NYSPI

Other Columbia University Medical Center Facilities

This protocol describes research conducted by the PI at other facilities/locations

No

## Lay Summary of Proposed Research

Lay Summary of Proposed Research

Age-related hearing loss (ARHL) is the third most common health condition affecting older adults after heart disease and arthritis and is the fifth leading cause of years lived with disability worldwide. Many hearing-impaired older adults avoid or withdraw from social contexts in which background noise will make

it difficult to communicate, resulting in social isolation and reduced communication with family and friends. Social isolation and loneliness have been linked to numerous adverse physical and mental health outcomes, including dementia, depression, and mortality, and they may also lead to declining physical activity and the development of the syndrome of frailty. Neuroimaging studies of ARHL have begun to elucidate the brain changes associated with degraded auditory input that provide plausible pathways by which chronic hearing loss may cause cognitive dysfunction and affective dysregulation. Specifically, compensatory activation increases in the cognitive control network (CCN) to support effortful listening may reduce the resources available for higher level tasks (14-15), while chronic deafferentation leads to atrophy of primary auditory regions and impaired downstream cognitive and affective processing of speech (16-17). In this project we hypothesize that untreated ARHL represents a distinct route to developing Late-life Depression (LLD) and that individuals with comorbid ARHL/LLD are unlikely to respond to treatments (i.e., antidepressant medication) that do not treat the underlying hearing problem. Initial studies suggest remediation of hearing loss using hearing aids or cochlear implantation may decrease depressive symptoms acutely and over the course of 6 to 12 months follow-up. However, the clinical significance of these findings is obscured by lack of rigorous control groups, failure to objectively document hearing aid compliance, and enrollment of study populations lacking syndromal depression or even a threshold symptom score. We propose to conduct the first clinical trial possessing these design features, while also incorporating neuropsychological and neuroimaging assessments that allow us to examine predictors and mechanisms of treatment response. 40 individuals will be recruited who are aged  $\geq 60$  years, diagnosed with a clinically significant depressive disorder, and have moderate ARHL with impaired speech discrimination. Comprehensive baseline psychiatric, audiometric, and neuropsychological assessment will be performed in addition to structural MRI (white matter hyperintensity [WMH] estimation and grey matter morphometry), diffusion imaging with tractography, and functional MRI (task-based and resting state connectivity). Participants then will be randomized to receive antidepressant medication (AD) treatment plus full amplification hearing aids or antidepressant medication plus low amplification hearing aids over a 12-week prospective trial. If participants do not wish change their antidepressant medication, they will be randomized to receive only full amplification hearing aids or low amplification hearing aids over a 12-week prospective trial. The baseline evaluation, including MRI scanning, will be repeated at the study endpoint. Data from this study could suggest a novel therapeutic strategy for LLD and thereby mitigate its public health burden, while also contributing to the increased recognition and treatment of ARHL more generally.

## Background, Significance and Rationale

### Background, Significance and Rationale

Age-related Hearing Loss (ARHL) contributes to the most prevalent and disabling neuropsychiatric conditions of later life: Late-Life Depression (LLD) and Cognitive Impairment (CI). ARHL is the third most common health condition affecting older adults after heart disease and arthritis (1) and is the fifth leading cause of years lived with disability worldwide (2). The prevalence of ARHL rises steeply with age, from 3% among adults 20-29 to 49% of adults ages 60-69 and >80% in those over 85 years (3-4). While historically considered a benign effect of aging or exclusively a quality of life issue, ARHL is in fact associated with significant psychological and medical morbidity, including social isolation, frailty, and falls (22). In addition, several analyses of epidemiological data sets (23-24), reviews (25) and meta-analyses (26), and a National Institute on Aging (NIA) workshop (27), have linked ARHL to cognitive decline in older adults.

Given its frequent sequelae of social isolation and withdrawal, ARHL has been linked to the development of depressive disorders in older adults (28-30). Gopinath et al (2009) found that depressive symptoms were associated with mild hearing loss (31), while Lee et al (2010) found that hearing thresholds measured with pure tone audiometry (PTA) were associated with scores on the Geriatric Depression Scale (GDS) (32). In an analysis of National Health and Nutrition Examination Survey (NHANES) data, self-reported hearing aid use was associated with significantly lower odds of LLD defined by a minimum score on the Patient Health Questionnaire (PHQ-9) (33). Finally, Contrera et al (2016) found in the Health Aging and Body Composition (HABC) Study that compared to individuals with no hearing impairment, participants with at least moderate (i.e., >40 dB) impairment had 23% lower odds of 'emotional vitality' (34).

Behavioral and neural mechanisms mediate the relationships between ARHL, LLD, and CI. Many hearing-impaired older adults avoid or withdraw from social contexts in which background noise makes communication difficult (5-6), resulting in social isolation and reduced communication with family and friends (7-8,35). Social isolation and loneliness have been linked to numerous adverse physical and mental health outcomes, including dementia (9-10), depression (11), and mortality (12), and they may also lead to declining physical activity and the development of the syndrome of frailty (13). Older adults with significant hearing loss report lower physical activity levels, perform worse on the Short Physical Performance Battery (SPPB), and have slowed gait speeds (36-38). Frailty and slowed gait speed exhibit significant, reciprocal relationships with both cognition (39) and LLD (40) and thus may represent an intermediate step in the progression from ARHL to CI and LLD.

Recent neuroimaging studies of ARHL have begun to elucidate compensatory and neuroplastic changes associated with degraded auditory input that provide plausible pathways by which chronic hearing loss may cause affective dysregulation, CI, and LLD. Deterioration of the peripheral hearing apparatus over time decreases input to primary auditory cortex, secondary association cortices, and the auditory thalamus, which is visualized in functional neuroimaging tasks as decreased neural activations to auditory stimuli (16,41). Blunted neural responses to sounds alters resting functional connectivity in the default mode network (DMN) (42) and leads to compensatory increased activations in the cognitive control network (CCN) to support effortful listening (14,43-47). This compensation may tax CCN capacity and cause manifest executive dysfunction (15), which is common in older depressed patients (48-51) and portends poor response to antidepressant medication as well as more chronic, recurrent course of illness (52-53). Chronic deafferentation of auditory and CCN networks is associated with atrophy of primary auditory cortex, PFC, and ACC (16-17,54-55). This atrophy may magnify the deleterious effects of acute compensatory shifts, creating a vicious cycle of declining hearing capacity, worsening executive function, and increasing risk for LLD and dementia.

Treating ARHL represents a novel therapeutic strategy for LLD/CI and may help older adults avoid unhealthy aging trajectories. Initial studies suggest remediation of hearing loss may decrease depressive symptoms acutely and over the course of 6-12 months follow-up (18-21), though other studies have failed to find any significant influence of hearing loss treatment on depression (56-57). Mulrow and Aguilar (1990) randomized N=194 subjects to receive hearing aids vs. wait list control and reported significantly increased self-reported quality of life and cognitive function as well as decreased depressive symptoms at 6 weeks and 4 months post-hearing aid prescription (58). The clinical significance of these findings is obscured by small sample sizes, lack of rigorous control groups, and the fact that the patients enrolled were not selected based

on the presence of syndromal depression or even a threshold symptom score. In addition, analyses of hearing aid use and depressive symptoms are plagued by inaccurate reporting, as studies only rarely utilize objective measures of when hearing aids are in place, turned on, and actually being used (59). These limitations highlight the need for rigorously designed, prospective studies of ARHL and LLD such as detailed in the present proposal.

We target patients with comorbid ARHL and LLD, proposing that they represent an etiologically distinct subgroup of older depressed patients who are not likely to respond to antidepressants. Hearing aids and cochlear implants are both available therapies for ARHL, and initial studies suggest that improving hearing improves quality of life and decreases social isolation (18). Should hearing loss prove to be a modifiable risk factor for depression, increasing its treatment rate could be an effective strategy for risk reduction given its near-universal prevalence in the elderly and low treatment levels. ARHL and LLD, both individually and together, are responsible for tremendous public health costs, including extensive disability, morbidity, and mortality. Data from this study could suggest a novel therapeutic strategy for LLD and thereby mitigate its public health burden, while also contributing to increased recognition and treatment of ARHL more generally

## Specific Aims and Hypotheses

### Specific Aims and Hypotheses

**Aim 1:** To investigate baseline relationships between ARHL, CCN circuit measures, and neuropsychiatric measures.

**Hypothesis 1:** More severe ARHL (higher thresholds on pure tone audiometry) will be associated with diminished connectivity and activation within the CCN, which themselves will be associated with poorer executive functioning and increased depressive symptoms.

**Aim 2:** To investigate whether augmentation of standard antidepressant medication treatment with hearing assistive devices is useful for the treatment of comorbid ARHL and LLD.

**Hypothesis 2:** AD + full amplification hearing aids will result in greater depressive symptom improvement (change on Hamilton Rating Scale for Depression [HRSD]) and higher response rates (proportion with Clinical Global Impressions—Improvement [CGI] score of 1 or 2 at endpoint), improved executive functioning, and increased pre-post CCN connectivity and activation compared to AD + low amplification hearing aids.

**Exploratory aims:** To explore the influence of hearing aid compliance (as measured by objective device usage logs) and change in social functioning (as measured by the Social Adjustment Scale—Self Report version [SAS-SR]) on pre-post change in depressive symptoms and executive functioning. We will also attempt to identify pre-treatment participant expectations related to hearing aids as well as participant-identified factors that influence hearing aid use and perceived effectiveness.

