4. Subjects will have follow up audiology appointments at Weeks 2, 6, and 12, during which their questions about hearing aid usage will be answered and the data log will be checked and reset. At Week 6, if the hearing aid devices are functioning well and the patient is meeting the usage requirement, the audiologist will ask if the patient would like to skip the Week 9 audiology visit and return at Week 12. However, if the patient's hearing aid use does not meet the requirement at Weeks 2 and/or 6 (as determined by the data log) or if there are any hearing aid complications, they will be scheduled for an audiology visit at Week 9. At Week 12, endpoint measures will be collected, which comprise the HHIE and repeat of audiological measurements from Week 0.

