9. Image processing and analysis: fMRI scans will be preprocessed using SPM 12 (slice-timing correction, motion correction, spatial normalization, and smoothing with 8mm FWHM). Region-of-interest (ROI) and whole brain analysis will be done with False Discovery Rate control (86). Regions within the CCN will constitute our ROI, given an association of decreased connectivity with LLD (87) and antidepressant response (88) (e.g., the DLPFC, dACC, supramarginal gyrus, putamen, and anterior insula) (89). Simon-Task fMRI: Preprocessed data will be entered to a subject-level regression model with 3 regressors (convolved with the canonical hemodynamic response and time derivative) corresponding to 1) congruent correct trials, 2) incongruent correct trials, and 3) incorrect trials. T-contrast images of "incongruent-minus-congruent" in each participant will be entered into a group-level mixed effects model. Resting MRI: Seed-based intrinsic functional connectivity will be carried out in the CONN toolbox v13 (90). Mean BOLD time series of each seed region will be correlated (Pearson's correlation) with timeseries of every other voxel's. Structural MRI: Morphometric measures (volume, thickness, surface area, etc) will be estimated using Freesurfer suite (91). WMH volumes will be estimated from FLAIR image using a semi-automated method by which WMH are seeded and passed through an iterative algorithm to yield WMH volumes. DWI: DWI will be preprocessing in MRtrix3 (92) (brain extraction, PCA-based denoising (93), eddy current correction (94), distortion correction (95), tensor modeling fitting to get anisotropy and diffusivity measures). Two

analyses will be performed: probabilistic tractography within the CCN ROIs (as above, 92), and voxel-based morphometry optimized to WM tracts (Tract-Based Spatial Statistics) (96). For probabilistic tractography, structural connection strength will be indexed by number of estimated WM streamlines (NOS; validated quantification of WM projection strength) (97). Further, quantitative nature of tractography will be enhanced by filtering out non-biologically plausible (false-positive) streamlines using Spherical-deconvolution Informed Filtering of Tractograms (SIFT) (98). For voxel-based morphometry (TBSS), diffusivity (MD) and anisotropy (FA) images will be warped into a study-specific template brain and projected onto alignment-invariant tract representation.

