## Data Analysis

Participants were randomized to receive hearing aid treatment vs. sham, and analysis of covariance (ANCOVA) was used to analyze the between-group differences (i.e., active-sham effect) on hearing, psychiatric, functional, and cognitive outcomes. For each measure (i.e., HHIE), the outcome modeled was the change from baseline (Week 0) to the end of study (Week 12) with predictors including baseline HHIE, group (active vs. sham), and covariates of age and education. Encompassing all participants (including those randomized to sham), this model provides baseline adjusted estimates of change within group, i.e. the difference from pre- to post-randomization for the active group, the difference from pre- to post-randomization for the Sham group, and the randomization effect between groups (active-sham effect). Differences in the number of hours of hearing aid usage between groups (active vs. sham) by time (Week 2, 6, 12) was analyzed using an analysis of variance (ANOVA) by including the predictors of group, time, and group by time interaction.

Lastly, association analyses were performed between audiometric measures (PTA and SDS) and mean FA and RD of the specified DTI ROIs using partial correlations and adjusting for age and gender as covariates. The same association analyses were performed between audiometric measures and cortical thickness of our T1 ROIs, adjusting for age, gender, and intracranial volume. Given the small sample size, the exploratory analyses did not control for multiple comparisons.

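### Neither document designates a primary outcome: Hypothesis 2 lists four or five unranked claims, and the SAP repeats one ANCOVA across four outcome domains with no multiplicity rule for the arm comparisons

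*Protocol*

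**What the plan says.** Hypothesis 2 (Protocol, Specific Aims and Hypotheses) is a single sentence. It says the full-amplification arm "will result in greater depressive symptom improvement (change on Hamilton Rating Scale for Depression [HRSD]) and higher response rates", where response is a CGI "score of 1 or 2 at endpoint". It then adds "improved executive functioning, and increased pre-post CCN connectivity and activation compared to AD + low amplification hearing aids". No component is called primary or secondary. The only aims labelled exploratory are those on device compliance, social functioning, and participant expectations and views of the devices, so Hypothesis 2 stands outside that label.

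In the SAP (Data Analysis), "analysis of covariance (ANCOVA) was used to analyze the between-group differences (i.e., active-sham effect) on hearing, psychiatric, functional, and cognitive outcomes". The model is then defined through one example: "For each measure (i.e., HHIE), the outcome modeled was the change from baseline (Week 0) to the end of study (Week 12". Its predictors are baseline value, group, age and education. HRSD is not mentioned by name.

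On multiplicity the SAP has one sentence, placed after the correlations between audiometry and imaging: "Given the small sample size, the exploratory analyses did not control for multiple comparisons". The Protocol (MRI procedures) specifies False Discovery Rate (FDR) control for region-of-interest and whole-brain imaging analyses. Neither document gives a multiplicity rule for the randomised ANCOVAs.

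**The concern.** A trial with several outcomes needs to say in advance which result decides its question. Here Aim 2 has a directional hypothesis with several components, and an analysis plan that treats every measure alike. Without a hierarchy, nobody can say from these documents what pattern of results would support Hypothesis 2, or what would count against it. A favourable result on one measure could be given prominence after the fact, and the error rate attached to that claim would not be the nominal one.

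The two documents also describe different families of tests. Hypothesis 2 includes a binary CGI response and CCN measures, yet the SAP gives no binary analysis and no between-arm CCN analysis. The SAP's ANCOVA family includes hearing and functional measures that Hypothesis 2 does not mention. So the SAP cannot be used to infer which outcome the investigators regarded as decisive.

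**Working it through.** **The plan's own figures.** The Protocol (Description of Subject Population) gives 32 completers from 40 enrolled, an implied loss of 1 − 32/40 = 20%. No significance level, power, effect size or SD accompanies these numbers, so the 32 cannot be reproduced. No family-wise error rate is stated either.

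**Assumptions.** Two-sided 0.05 per test; no true effect on any measure counted; any single significant result could be claimed; and, for correlated tests, equal correlation ρ between test statistics.

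**Counting the tests.**
- Hypothesis 2: HRSD change, CGI response, executive functioning and CCN make 4 claims, or 5 if connectivity and activation are separate. Each CCN claim is counted once at 5%, on the footing that FDR control within imaging keeps it there when nothing is going on.
- ANCOVA battery, non-hearing measures with a baseline (Protocol, Study Assessments): HRSD, CGI-Severity, IDS-SR, SAS-SR (4); SPPB, gait speed, activity kcal, WHODAS 2.0, ECog (5); RBANS-H total, Dimensional Change Card Sort, Flanker (3). Total 12. This is a tally, because the SAP does not list its measures.
- Left out: CGI-Improvement, which has no baseline and so cannot enter a change-from-baseline model. Also left out are the hearing measures. At Week 12, "endpoint measures will be collected, which comprise the HHIE and repeat of audiological measurements from Week 0", and these are expected to differ by design because low amplification is programmed not to improve speech discrimination substantively.

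**Formula.** For k independent tests, P(at least one false positive) = 1 − 0.95^k. For example, 1 − 0.95^4 = 0.186, 1 − 0.95^5 = 0.226 and 1 − 0.95^12 = 0.460. Values for correlated tests come from numerical integration over a shared normal factor.

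| Family | k | Independent | ρ = 0.3 | ρ = 0.5 | ρ = 0.7 |
|---|---|---|---|---|---|
| Hypothesis 2 | 4 | 18.5% | 17.4% | 15.6% | 13.0% |
| Hypothesis 2, CCN split | 5 | 22.6% | 20.9% | 18.3% | 14.8% |
| Non-hearing measures | 12 | 46.0% | 39.7% | 31.9% | 23.2% |

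The independent-test figure passes 50% only at k = 14, since ln 0.5 / ln 0.95 = 13.5. At a different per-test level, the independent figure for k = 4 would be 3.9% at 0.01 and 34.4% at 0.10.

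**Why one primary rather than several co-primaries.** The Protocol says 20 of 40 participants receive low amplification, so about 16 completers per arm are expected. With the unadjusted two-group normal approximation at 80% power, the detectable difference is (1.96 + 0.84) × √(2/16) = 0.99 SD. Bonferroni over 4 claims (0.05/4 = 0.0125) raises it to 1.18 SD, and over 5 (0.05/5 = 0.01) to 1.21 SD. At a true difference of 0.99 SD, power falls from 80% to 62% or 59%. Baseline adjustment would reduce all the detectable differences.

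**The case against.** Several stronger readings are tempting, and the documents do not support them.

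- A reader might infer that the ANCOVAs are unadjusted. They adjust for baseline, age and education; only a multiplicity rule is missing.
- A reader might infer that the SAP expressly declines multiplicity control for the randomised comparisons. Its sentence refers to exploratory analyses and follows the imaging correlations. On the arm comparisons the SAP is silent, and the Protocol does provide FDR control for imaging.
- A reader might infer that a chance positive is more likely than not. Counting 17 independent measures gives 1 − 0.95^17 = 58%. That tally includes hearing measures expected to differ by design and CGI-Improvement, which does not fit the model. It also treats overlapping depression scales as independent, and gait is already a component of SPPB.
- A reader might infer that HHIE has displaced HRSD, or lies outside Aim 2. HHIE illustrates a model meant for each measure, and Aim 2 concerns comorbid hearing loss and depression.

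Two further objections carry weight. Hypothesis 2 joins its components with "and". If all had to succeed, the false-positive rate would be at most 5%, so the percentages above apply only if one success is enough. Neither document says which rule holds, and that is itself the gap. Also, the Protocol form has no statistical section, and the grant application it refers to was not available. A primary outcome may be named there or in the registry, so the point is limited to these two documents.

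**Conclusion.** The point stands in this form: the Protocol and SAP designate no primary outcome, state no success rule for Hypothesis 2, and give no multiplicity rule for the arm comparisons. Under the assumptions listed, the chance of at least one false positive is about 16–23% for the 4–5 claims of Hypothesis 2, and about 32–46% for roughly 12 non-hearing measures (independent tests down to ρ = 0.5). Stronger correlation lowers these, to 13–15% and 23% at ρ = 0.7, still well above 5%. The figures depend on an unstated significance level, a tallied list of measures, and the reading that any one positive could be claimed. The absence of a stated criterion depends on none of these.

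**What to change.** 1. State in the SAP that the primary arm comparison is full versus low amplification on change in 24-item HRSD from Week 0 to Week 12, two-sided 0.05, justified by its first position in Hypothesis 2. If the grant or registry already names a primary outcome, carry that one over instead.
2. The SAP is written in the past tense, so record the date of the designation and whether unblinded data had been seen. If they had, label the designation post hoc; it cannot then restore error control.
3. Make CGI response and executive functioning secondary. Add an analysis of CGI response as a binary outcome, and tie executive functioning to the Dimensional Change Card Sort and Flanker tests. Apply Holm to these three tests, with thresholds 0.05/3 = 0.0167, 0.05/2 = 0.025 and 0.05.
4. Keep the Protocol's FDR control for CCN imaging.
5. Report all other measures, including HHIE, as estimates with 95% confidence intervals and no confirmatory claim.

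This needs SAP text and one added binary analysis, but no new data or participants. The cost is that an isolated positive on a measure outside the primary comparison could not be claimed as confirmatory.
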